#### **IDMC Safety, Efficacy and PK Review - Part 3**

The IDMC will continue to review safety, efficacy and PK data available after every 10 patients are enrolled and treated for at least 2 cycles.

In general, if the SRC or the IDMC determine at any time that the dose should be reduced for safety reasons, a lower dose of Debio 1562 will be explored.

## 5. STUDY TREATMENT

### 5.1. Description of Study Treatment

The investigational study drug, Debio 1562, will be provided by the Sponsor in 20 mL glass vials each containing 5 mL of a protein concentration of 8.0 mg/mL Debio 1562 [REDACTED]

Rituximab will be supplied as a commercially available formulation. Please refer to the rituximab prescribing information.

### 5.2. Debio 1562 Packaging and Labeling

The Debio 1562 container [REDACTED] The label [REDACTED] will include the necessary information as required by the country in which it is being used.

### 5.3. Storage, Handling, and Accountability

Specific details regarding storage and handling of Debio 1562 and rituximab can be found in the Pharmacy Manual.

Additionally, please refer to the rituximab prescribing information regarding the proper storage and handling of this drug.

Accountability and shipping documents for all drugs supplied by the Sponsor must be maintained by the Principal Investigator or designee (e.g., the study pharmacist). The Investigator or designee must maintain an accurate record of the receipt and dispensing of Debio 1562 in a drug accountability log. These records must always be available for inspection, and a copy will be supplied to the Sponsor, on request. Information recorded on these accountability and shipping documents will include quantities received, dates and amount dispensed, the recorder's initials, patient number to whom the drug was administered, lot number of drug administered, and drug lost, damaged, or destroyed.

Upon completion of the study, all Debio 1562 dispatched to a site must be accounted for and unused supplies destroyed according to the site's Standard Operating Procedures upon Sponsor approval. If the site cannot destroy onsite, return of unused supplies to the Sponsor can be arranged. The original drug reconciliation records shall be maintained at the site and a copy collected and sent to the Sponsor once a representative of the company has confirmed the drug accountability. The pharmacy shall maintain accurate records of all study drugs that have been received, stored, dispensed, destroyed, and used. The electronic Case Report Form (eCRF) shall also record details of study drug administration such as date and time of administration.

Drug accountability will be monitored regularly.

### 5.4. Study Treatment Compliance

Debio 1562 and rituximab supplied for the study may not be used for any purpose other than the study or administered other than as described in this protocol.

Source documents must capture the dates when drug is dispensed and the initials of the person preparing the dose as well as the volumes and doses dispensed, patient number, lot number, and expiration date if available of the drug administered.

Under no circumstances is the Investigator allowed to release Debio 1562 supplies to any physician not named as part of the study (e.g., not named in the FDA Form 1572) or to administer these supplies to a patient not enrolled in this study. If investigational supplies are to be dispensed from any facility other than that supervised directly by the Principal Investigator (i.e., hospital pharmacy, satellite pharmacy), it is the responsibility of the Principal Investigator to ensure that all Debio 1562 is maintained in the manner described in the Pharmacy Manual.

For Debio 1562, two different drug lots cannot be mixed in a single dose administration.

## **5.5. Assignment of Patient Number**

Patient numbers are assigned in sequential order as patients sign informed consent to participate.

Patients who have consented to the study and who have received at least one dose of study treatment will be considered enrolled.

Patients who are issued a patient number, but who do not successfully complete the screening process and who do not receive a dose of study treatment will be considered a screen failure.

A patient number that has been issued for a given patient who failed screening will not be re-issued for another patient, but can be re-issued to the same patient if he/she is re-screened for the study at a later date.

## **5.6. Blinding**

Not applicable as this is an open-label study.

## **5.7. Drug Preparation and Administration**

Debio 1562 is an experimental anticancer drug, and as with other potentially toxic compounds, caution should be exercised when handling this compound. It is recommended that gloves and protective garments be worn during preparation. Similar precautions should be taken when handling rituximab. Refer to the Pharmacy Manual and rituximab package insert for more information.

For logistical reasons (such as holidays, weekends, etc.), changes of  $\pm$  3 days in the start of any cycle of study treatment are permitted. Similarly, intra-cycle administrations on Day 8 and Day 15 in Cohort B patient can have a window of -1 day to +3 days for logistical reasons; however, every two administrations need to have a minimal interval of 5 days.

### **5.7.1. Pre- and Post -Infusion Prophylaxis**

Prior to receiving treatment with Debio 1562 and rituximab, patients will be given dexamethasone IV at 8 mg (or equivalent), acetaminophen PO or IV 325 – 650 mg, and an antihistamine (e.g. 25-50 mg diphenhydramine or equivalent) approximately 30-60 minutes prior to the Debio 1562 infusion. Patients will be instructed to take oral dexamethasone at 8 mg/day on Days 2 and 3, following the infusion. If any patient requires more intensive treatment to prevent infusion reaction, investigators may modify the regimen accordingly.

In patients with poor bone-marrow functional reserve or as part of the management of previously occurring cytopenias treatment (See [Section 5.8.2](#)), granulocyte colony-stimulating factor support could be used in accordance with either the American Society of Clinical Oncology ([Smith 2015](#)), or European Society of Medical Oncology guidelines ([Crawford 2010](#)), as determined by institutional or regional practice.

Any patient experiencing TLS or at risk for TLS should be managed according to institutional practice. Patients with high tumor burden and/or high circulating lymphocyte counts ( $> 25 \times 10^9/L$ ) are at greater risk for TLS and should be adequately hydrated beginning 12 - 24 hours prior to the infusion of Debio 1562 (e.g. 2 L within 12 - 24 hours prior to infusion – roughly 170 cc every two hours).

Patients should receive prophylactic antiviral treatment as per institutional guidelines.

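### The example hydration volume, start window and rate for patients at greater risk of tumour lysis agree only for a start about 24 hours before infusion; a later start run at the stated rate gives less than 2 L

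*Protocol*

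**What the plan says.** Protocol Section 5.7.1 singles out patients with high tumour burden and/or circulating lymphocytes above 25 x 10^9/L as being at greater risk of TLS. It says they "should be adequately hydrated beginning 12 - 24 hours prior to the infusion of Debio 1562". A parenthesis introduced as an example then gives a volume, "2 L within 12 - 24 hours prior to infusion", followed after a dash by a rate, "roughly 170 cc every two hours".

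Section 5.8.1 repeats the same instruction, window, volume and rate. Neither section gives a different rate for a start later than 24 hours before infusion. Both also contain the general rule: "Any patient experiencing TLS or at risk for TLS should be managed according to institutional practice".

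Section 1.9 (Risk Minimization Measures) names hydration before the infusion as a measure against TLS, but gives no volume, window or rate. The example in Sections 5.7.1 and 5.8.1 is the only numerical hydration guidance in the documents supplied.

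**The concern.** The sentence links three quantities: when hydration starts, how much is given and how fast. Any two of them fix the third. Because the start time is a range from 12 to 24 hours, a single volume and a single constant rate cannot both hold across it. The text does not say which start time the rate was worked out for.

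Two sites could both start 12 hours ahead, as the text permits, and both believe they were following the example. One working to the volume would give 2 L; one working to the rate would give about half of that. Section 5.8.1 says that TLS may be fatal and that signs of it have been seen with Debio 1562, so the example should at least be consistent with itself. Because the wording is the same in both sections, comparing one with the other does not reveal the mismatch.

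**Working it through.** **Inputs (Protocol Sections 5.7.1 and 5.8.1, identical in both)**
- Start of hydration: 12 to 24 hours before the infusion
- Example volume: 2 L = 2,000 mL
- Example rate: 170 mL per 2 hours, so 170 / 2 = 85 mL per hour

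**Reproducing the plan's own figure**
- Volume delivered = 85 mL/h x hours available.
- With a 24-hour start: 85 x 24 = 2,040 mL, which is 2% above 2 L.
- In reverse: 2,000 mL over 24 hours is 2,000 / 12 = 167 mL per two hours, which rounds to the stated 170.

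The example therefore reproduces at the 24-hour end of the window.

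**The rest of the window**
- Time to reach 2 L at the stated rate = 2,000 / 85 = 23.5 hours.

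| Start before infusion | Volume at the stated rate | Share of 2 L |
|---|---|---|
| 24 h | 85 x 24 = 2,040 mL | 102% |
| 20 h | 85 x 20 = 1,700 mL | 85% |
| 18 h | 85 x 18 = 1,530 mL | 76.5% |
| 16 h | 85 x 16 = 1,360 mL | 68% |
| 12 h | 85 x 12 = 1,020 mL | 51% |

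The shortfall is 23.5% with an 18-hour start and 49% with a 12-hour start.

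**Other readings tried**
- If the window means the interval from 24 to 12 hours before infusion, it is still 12 hours long, and the rate still gives 85 x 12 = 1,020 mL.
- If fluid is given as separate 170 mL portions with one at each end of a 12-hour period, that is 7 x 170 = 1,190 mL, 40.5% short.
- The approximate wording of the rate covers the 2% difference at 24 hours. It cannot cover a difference of 40% to 49%.

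None of these readings makes the three quantities agree across the window.

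**The case against.** A reader might infer that the protocol causes patients started at 12 hours to receive half the intended fluid, and so contains a patient-safety defect. The documents do not support that, for four reasons.

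- **The volume stands beside the rate.** The shortfall needs a site to start well short of 24 hours, follow the rate and disregard the 2 L in the same parenthesis.
- **The figures are illustrative.** They are offered as an example, the rate is approximate, and both sections leave patients at risk of TLS to institutional practice. The operative instruction is adequate hydration. The measure in Section 1.9 does not depend on the example's rate, and it is paired with serum chemistry, which Appendices B and C schedule on Days 2 and 3 of Cycles 1 and 2.
- **The rate is not a miscalculation.** It is correctly rounded for a 24-hour start. The fault is that the example does not say it was worked for that case.
- **Little use of the text remains.** Sections 1.9 and 1.10.6 state that enrollment is complete, and Section 5.5 counts a patient as enrolled only after a first dose. No first infusions were therefore left under this version, and Section 5.8.1 ties rituximab-related TLS to the first infusion.

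All four points stand, and they limit the weight of the finding. They do not make the sentence consistent. The hydration instruction is not expressly confined to Cycle 1, nothing elsewhere in the documents resolves the mismatch, and the wording could be carried into later documents.

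**Conclusion.** The point holds as a minor internal inconsistency. Volume, window and rate in Sections 5.7.1 and 5.8.1 agree only for a start about 24 hours before infusion. At the stated rate the volume falls to about 1.53 L with an 18-hour start and about 1.02 L with a 12-hour start, against a stated 2 L.

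These sizes assume a constant rate from the start of hydration to the infusion, and a site that follows the rate instead of the volume. A site that follows the volume has no shortfall, and one that follows its own institutional practice may use neither figure.

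The documents do not show which of the two figures is intended, and this review takes no position on it. No endpoint, analysis population, sample size, decision rule or other statistical quantity is affected. The correction is desirable but not essential.

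**What to change.** Reconcile the volume, start window and rate in Sections 5.7.1 and 5.8.1 together, so that they agree across the stated window. Two ways of doing this leave the clinical content to the sponsor: state the start time to which the rate applies, or keep only one of volume and rate. The sponsor's clinicians should decide which figure is intended.

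The cost is one phrase changed in each of two sections. No analysis, data collection or SAP text needs to change.

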#### **5.7.2. Debio 1562 Preparation**

The total dose of Debio 1562 will be calculated based on each patient's body weight. The weight used for calculation should be obtained prior to first treatment and thereafter should only be modified for significant ( $\geq 10\%$ ) changes in body weight (not influenced by weight gain or loss attributed to fluid retention). Further information about dosing requirements is outlined in the Pharmacy Manual.

#### **5.7.3. Rituximab Preparation**

Rituximab will be prepared per label. Body weight at Cycle 1 Day 1 is to be used to calculate the body surface area ([Appendix J](#)), which will be used to determine the required rituximab dose. No dose modifications are foreseen unless the patient's body weight changes by  $\pm 10\%$  from baseline.

#### **5.7.4. Administration**

##### **5.7.4.1. Debio 1562**

After the pre-infusion prophylaxis regimen is given, Debio 1562 will be administered as follows:

- At 0.7 mg/kg, or other applicable dose as determined by the SRC, as an IV infusion on Day 1 of a 21-day cycle for safety run-in (study Part 1);
- At 0.7 mg/kg, or other applicable dose as determined by the IDMC, as an IV infusion on Day 1 of a 21-day cycle for cohort A (study Part 2);
- At 0.4, 0.2, 0.2 mg/kg, or another applicable dosing regimen as determined by the IDMC, as an IV infusion on Day 1, Day 8 and Day 15, respectively, of a 21-day cycle for cohort B (study Part 2);
- During Part 3 of the study, Debio 1562 will be administered according to the selected dosing regimen(s) studied in Part 2.
- During the COVID-19 pandemic, patients on the Debio 1562 QW regimen can be switched to the Q3W regimen. If a switch to the Q3W regimen is considered by the treating physician to be in the best interest of a given patient to mitigate the COVID-19 risk, the following should be observed:

- the patient must terminate his/her ongoing weekly administration cycle before switching to the Q3W regimen. For instance, if the patient received his/her first weekly administration of 0.4 mg/kg (D1), he/she should continue to receive weekly treatment until the end of that cycle. Only then can the patient start the Q3W dosing regimen (0.7 mg/kg), as an IV infusion on Day 1 of a 21-day cycle – similarly as for cohort A);
- patients who switch should continue to receive the Q3W regimen, following Cohort A treatment schedule for the remainder of the study.

Debio 1562 should be administered first at Day 1 of each cycle, followed by rituximab. An IV tubing administration set with a 0.22 micron in-line filter will be used for infusion.

Initially, Debio 1562 should be administered at a rate of 1 mg/min; after a continuous 30 minutes of infusion, the rate can be increased to 3 mg/min if well tolerated. If well tolerated after a continuous 30 minutes of infusion at 3 mg/min, the rate may be increased to 5 mg/min. Subsequent infusions may be delivered at the tolerated rate. The overall length of infusion will vary depending on dose and patient tolerability; the infusion time will range from approximately 15 to 60 minutes. Following infusion, the IV line should be flushed with normal saline as needed to ensure delivery of the full dose.

Patients will be carefully observed during each infusion and vital signs taken as outlined in the Schedule of Events ([Appendix A](#), [Appendix B](#), [Appendix C](#)).

#### **5.7.4.2. Rituximab**

Rituximab will be administered at a dose of  $375 \text{ mg/m}^2$  at Day 1 of each 21-day cycle, after administration of Debio 1562 (no minimum time-interval is required between finishing Debio 1562 and starting rituximab), throughout the study as follows:

- Dose 1 (Cycle 1, Day 1): infusion will be initiated at a rate of 50 mg/h and if tolerated, the rate will be increased in increments of 50 mg/h every 30 minutes up to a maximum of 400 mg/h.
- For subsequent doses, the infusion will begin at a rate of 100 mg/h and, if tolerated, the rate will be increased in increments of 100 mg/h every 30 minutes up to 400 mg/h.

Rituximab will be infused over approximately four hours.

#### **5.7.4.3. Post-infusion monitoring period**

Patients will remain in the clinic under monitoring for four hours after completion of the rituximab infusion for the first cycle. Post-administration safety monitoring could potentially be shortened (i.e. < 4 hours but at least 1 hour) following subsequent administration of rituximab, based on the judgement of the investigator. Patients receiving Debio 1562 only, i.e., on Day 8 and Day 15 for the QW dosing schedule or due to rituximab intolerance, will also remain in the clinic under monitoring for one hour for all cycles.

#### **5.7.4.4. Clinic Visit Duration**

The length of time that patients will be expected to remain in clinic for protocol procedures will vary. The two longest clinic visits (approximately nine hours) are expected to occur on:

- Day 1 in Cycles 1 and 3 during safety run-in (Part 1)
- Day 1 in Cycles 1 and 2 in cohorts A and B (Part 2 and Part 3)

### **5.7.5. Management of Potential Infusion-related Reactions**

Despite pre-infusion prophylaxis, some patients receiving Debio 1562 or rituximab have experienced infusion-related reactions.

Mild to moderate infusion-related reactions consisting of chills and rigors have been experienced by some patients receiving Debio 1562.

Severe infusion reactions have been reported by some patients receiving rituximab. Infusion reactions consisting of fever, chills/rigors, nausea, pruritus, angioedema, hypotension, headache, bronchospasm, urticaria, rash, vomiting, myalgia, dizziness, or hypertension may typically occur within 30 to 120 minutes of beginning the first rituximab infusion and resolve with slowing or interruption of the infusion and with supportive care (diphenhydramine, acetaminophen, and intravenous saline). The incidence of infusion reactions is highest during the first infusion and decreased with each subsequent infusion. As such, all patients will receive pre-infusion prophylaxis. Additionally, patients will be provided oral steroids to be taken on Days 2 and 3 of each cycle.

Some patients treated with IV infusions of therapeutic drugs have experienced concurrent infusion-related reactions (refer to CTCAE Version 4.03). The signs and symptoms may vary and include for example, headache, fever, facial flushing, pruritus, myalgia, nausea, chest tightness, dyspnea, vomiting, erythema, abdominal discomfort, diaphoresis, shivers, lightheadedness, hypotension, palpitations, and somnolence. Anaphylaxis might occur at any time during an infusion. Before any infusion is started, appropriate medical personnel, medication (e.g. epinephrine, inhaled beta agonists, antihistamines, and corticosteroids), and other required resources to treat anaphylaxis must be readily available. In general, Investigators should manage acute allergic or hypersensitivity reactions according to Institutional practices. General, suggested guidelines for the management of acute infusion-related reactions and for subsequent retreatment are provided in [Table 4](#). Delayed infusion-related reactions may occur; therefore patients should be advised to seek immediate medical treatment if symptoms newly develop and/or recur after discharge from clinic.

Patients who experience a  $\geq$  Grade 2 infusion-related reaction during or immediately following administration of Debio 1562 should have blood drawn within three hours of the onset of the reaction and one week later for determination of drug concentration (PK) and antibodies to Debio 1562 (ADA) ([Sections 6.1.1](#) and [6.2.1](#)).

**Table 4: Management Guidelines for Potential Infusion-related Reactions**

Infusion Reaction CTCAE v4.03 Severity Grade	Management
Grade 1: Mild, transient reaction	
 
Maintain infusion rate unless progression of symptoms to <math>\geq</math> Grade 2; if symptoms worsen, refer to guidelines below
 
Promethazine 150 mg by mouth (PO) per day (every 4 hours [Q4h]) as needed (prn) for nausea (or equivalent)
 
Diphenhydramine 25-50 mg PO or IV prn (or equivalent)
 
Methylprednisolone 125 mg (or equivalent) IV prn
 

Grade 2: Moderate	
 
Interrupt infusion and disconnect infusion tubing from patient
 
Promethazine 150 mg PO per day (Q4h) prn for nausea (or equivalent)
 
Diphenhydramine 25-50 mg PO or IV prn (or equivalent)
 
Acetaminophen 650 mg PO prn (or equivalent)
 
Methylprednisolone 125 mg (or equivalent) IV prn
 
After recovery from symptoms, resume the infusion at 50% of the previous rate and if no further symptoms appear, gradually increase rate of infusion (do not surpass maximum infusion rate allowed per protocol) until infusion is completed.
 
For subsequent dosing in future cycles, patients should be pre-medicated with Dexamethasone 8 mg PO twice daily (BID) (or equivalent) the day prior to drug administration and Acetaminophen 650 mg PO (or equivalent) and Diphenhydramine 25-50 mg PO 30-60 minutes (or equivalent) prior to dosing.
 

Grade 3: Severe, prolonged reaction not rapidly responsive to symptomatic medication and/or brief interruption of infusion; recurrence of symptoms following initial improvement; hospitalization indicated for clinical sequelae	
 
Stop infusion and disconnect infusion tubing from patient
 
Administer Diphenhydramine (25-50 mg) IV (or equivalent)
 
Administer normal saline, epinephrine (0.2-0.5 mL of a 1:1000 dilution [0.2-0.5 mg] subcutaneously [SC] or intramuscularly [IM]) (or equivalent) and bronchodilators (nebulized albuterol, 2.5-5 mg in 3 mL of saline) as medically indicated
 
Consider IV steroids (methylprednisolone (or equivalent) up to 0.5 mg/kg every 6 hours [Q6h]) to prevent recurrent or ongoing reactions
 
Advise patient to seek emergency treatment and notify investigator/clinic if the infusion-related symptoms recur after discharge from clinic.
 
Report as an SAE
 
Investigators should confer with the sponsor regarding retreatment of the patient. If the investigator and sponsor agree that the patient could be re-challenged, then prophylaxis for an infusion-related reaction should occur in all subsequent cycles. For this, patients should be pre-medicated with Dexamethasone 8 mg PO BID the day prior drug administration and Acetaminophen 650 mg PO and Diphenhydramine 25-50 mg PO 30-60 minutes prior to dosing.
 

Grade 4: Life-threatening consequences, urgent intervention indicated	
 
Immediately stop infusion and disconnect infusion tubing from patient
 
Permanently discontinue study medication treatment
 
Administer Diphenhydramine 50 mg IV (or equivalent)
 
Administer normal saline, epinephrine (0.2-0.5 mL of a 1:1000 dilution (0.2-0.5 mg) SC or IM (or equivalent)
 
Administer bronchodilators (nebulized albuterol, 2.5-5 mg in 3 mL of saline) as medically indicated
 
Administer IV steroids (methylprednisolone up to 0.5 mg/kg Q 6h) (or equivalent) to prevent recurrent or ongoing reactions
 
Report as a serious adverse event
 
Remove patient from study.
 

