#### 5.9.2.1 Adverse Events Requiring Permanent Study Treatment Discontinuation

Both Debio 1562 and rituximab should be permanently discontinued in the case of the following treatment-related events:

- $\geq$  Grade 3 cardiac event
- $\geq$  Grade 3 cutaneous reactions related to rituximab treatment
- Other non-hematologic events of Grade 4 severity
- Grade 4 thrombocytopenia lasting  $>7$  days
- $\geq$  Grade 3 neuropathy
- Dose delay  $> 21$  days due to unmet retreatment criteria

Rituximab should be permanently discontinued in patients experiencing the AEs listed in [Table 6](#).

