## **5.10. Removal of Patients from the Study**

The patient is free to withdraw consent and discontinue participation in the study at any time without prejudice to further treatment. Patients may be discontinued from study treatment, and continue to be followed per protocol, or they may be removed from the study altogether.

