### **5.10.1. Discontinuation from Study Treatment**

Patients may be withdrawn from study treatment at any time at their own request, or they may be withdrawn at the discretion of the Investigator or Sponsor for safety or non-compliance to the protocol.

Reasons for permanent discontinuation of both study drugs may include the following:

- Radiological PD
- Clinical progression
- Withdrawal of consent to study treatment, but agrees to the protocol-defined follow up

- AE
- Investigator decision
- Study terminated by Sponsor
- Major protocol deviation or non-compliance
- Patient becomes pregnant
- Death
- Other

Depending on the disease state and the tumor response, patients who permanently discontinue study treatment will enter into the response and survival follow-up portion of the study: patients who had discontinued study treatment due to PD will be followed-up for survival every 12 weeks ( $\pm$  4 weeks) for up to one year from the last patient's first dose (Cycle 1 Day 1); Patients who discontinued the treatment for reasons other than PD (including treatment completion) will be followed by radiographic assessment every 12 weeks ( $\pm$  4 weeks) from the time of the patient's last on-study tumor assessment until documentation of PD or beginning of subsequent anti-cancer therapy (regimen and start date to be recorded in the EDC). After the response follow-up, patients will enter into the survival follow-up. Patients will not be required to visit the clinic for survival follow-up.

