## 9. ASSESSMENT OF SAFETY

### 9.1. Recording Adverse Events and Serious Adverse Events

AEs (including SAEs) will be documented on the AE eCRF and monitored continuously throughout the study from the time informed consent is obtained until 30 days after the patient's last study treatment or until the event has resolved or stabilized or an outcome has been reached, whichever comes first.

For patients who discontinue study treatment due to a study-related AE, the reporting time-period may be extended. These patients must be followed at least once a week for four weeks, and subsequently at 4-week intervals until resolution or stabilization of the AE or laboratory abnormality, whichever comes first ([Section 5.10.1](#)).

If the Investigator considers it necessary to report an AE considered study drug related in a patient occurring after the end of study, he or she should contact the Sponsor to determine how the AE should be documented and reported.

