e) Radiographic tumor evaluation by CT or PET-CT scan of chest, neck, abdomen and pelvis will be performed within 28 days prior to first dose of study treatment. The anatomical regions to be assessed radiographically post baseline will be determined by individual patients' extent of disease. Whenever possible, the same radiographic scan assessment used at screening (e.g., PET-CT) should be used at all subsequent radiographic evaluations.

f) Post-baseline disease assessments will be performed every 6 weeks from Cycle 1, Day 1 and will not shift due to dose delays. For patients who are exceptionally granted continued study treatment after completion of 6 cycles, repeat radiographic tumor response assessments can be performed as per local institutional care practice. Ideally, repeat assessments should continue at 6-week ( $\pm$  1 week) intervals and should not be longer than 12-weeks ( $\pm$  4 weeks). Periodic tumor assessment will be conducted using the same imaging modality of prior cycles of treatment until PD, start of any new anti-cancer therapy, or death.

g) Patients discontinuing Debio 1562 for reasons other than PD will have subsequent clinic visits for radiographic assessment every 12 weeks ( $\pm$  4 weeks) from the time of their last on-study tumor assessment until PD or starting a subsequent anti-cancer therapy. For patients who discontinue for PD, no radiographic scans will be required at the EOT visit or the follow-up visits. All patients will be followed for survival every 12 weeks ( $\pm$  4 weeks) from the time of the 30-day safety Follow-up visit, for up to one year from the last patient's first dose (Cycle 1 Day 1). Patients will not be required to visit the clinic for survival follow-up.

h) Patients must have available a pathology-informed tumor biopsy sample representative of the current disease, [REDACTED].

i) If applicable, a bone marrow biopsy or aspirate will be performed within 3 months prior to first dose. A repeat bone marrow biopsy or aspirate will be required for patients with bone marrow infiltration at baseline who have a CR by imaging and physical examination, and will, in case possible and deemed acceptable by the Investigator, be performed every 6 weeks as clinically indicated. In order to better understand the effect of Debio 1562 on WBCs, bone marrow biopsies/aspirates may also be requested for those patients who experience grade 4 cytopenias.

[REDACTED]

[REDACTED]

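### The Grade 4 row of Table 4 tells sites to take the patient off the study, which contradicts the sections that stop treatment but keep follow-up

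*Protocol*

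**What the plan says.** Table 4 in Protocol Section 5.7.5 sets out management by CTCAE grade. The Grade 4 row has one bullet that stops study medication permanently, one that requires a serious adverse event report, and a last one that reads "Remove patient from study". The section introduces the table with the words "General, suggested guidelines for the management of acute infusion-related reactions and for subsequent retreatment are provided in" Table 4.

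Other parts of the protocol deal with the same patient:

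- **Section 5.9.2.1** lists "Other non-hematologic events of Grade 4 severity" among the treatment-related events for which both drugs are stopped permanently. It does not mention leaving the study.
- **Section 5.10** separates the two outcomes: "Patients may be discontinued from study treatment, and continue to be followed per protocol, or they may be removed from the study altogether".
- **Section 5.10.1** names an adverse event as a reason to stop both drugs and says "patients who permanently discontinue study treatment will enter into the response and survival follow-up portion of the study", subject to disease state and tumor response. If the reason is not progression, scans continue every 12 weeks (± 4).
- **Section 5.10.2** gives the reasons for leaving the study. Adverse event is not among them, but investigator decision and a catch-all category are.
- **Section 9.1** says of patients who stop for a study-related adverse event: "These patients must be followed at least once a week for four weeks". After that the interval is four weeks, until the event resolves or stabilizes.
- **Section 5.7.5**, in the text before the table, says patients with a Grade 2 or worse reaction to Debio 1562 "should have blood drawn within three hours of the onset of the reaction and one week later", for drug concentration and antibodies.
- **Appendix B, footnote g** says "All patients will be followed for survival every 12 weeks" (± 4 weeks), starting from the 30-day safety visit. Appendices A and C match it.

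**The concern.** A site cannot take a patient off the study and also carry out the follow-up that the other sections require. The row already has its own bullet for stopping treatment, so the natural reading of the last bullet is that it adds something: the patient leaves the study.

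If a site acts on that reading, follow-up ends because of toxicity. What could be lost is the course of the reaction to resolution, the one-week PK and antibody sample (Debio 1562 reactions only), later scans and the survival contacts. The reaction itself is not lost, because the same row requires an SAE report. The time-to-event endpoints would be censored for a reason tied to treatment, which is the kind of censoring that Kaplan-Meier estimates assume away.

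**Working it through.** There is no planned figure to reproduce. The check sets the texts side by side, follows one patient through the SAP rules, and does one timing calculation.

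**1. Do the texts agree?**

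| Question | Table 4, Grade 4 | Rest of the protocol |
|---|---|---|
| Study drug | Stopped permanently | Stopped permanently (5.9.2.1) |
| Study participation | Removed | Continues (5.10.1) |
| Adverse event follow-up | Ends, if removal is literal | Weekly for four weeks, then 4-weekly (9.1) |
| One-week PK/antibody sample | Ends, if removal is literal | Required after a Debio 1562 reaction (5.7.5) |
| Scans | End, if removal is literal | Every 12 weeks if not stopped for progression (5.10.1) |
| Survival contact | Ends, if removal is literal | Every 12 weeks, all patients (Appendix B) |

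They agree on the drug and disagree on everything after it. SAP 10.1.2 sides with the rest of the protocol: it lists adverse event as a reason for treatment discontinuation but not for study discontinuation.

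**2. What would the SAP do with such a patient?** SAP 10.2 also summarizes PFS and OS for the All treated population, which needs only one dose of Debio 1562 (SAP 7.2).

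- *PFS, no post-baseline scan:* censoring rule 5 in SAP 10.2.4.1 censors at first dose, unless the patient died within 190 days. The SAP's window reproduces: 5 × (21 + 3) + 21 + 7 + 42 = 120 + 70 = 190 days.
- *PFS, reaction in a later cycle with scans available:* censored at the last adequate assessment if no progression or death is recorded.
- *OS:* censored at the last date known alive (SAP 10.2.4.4).

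**3. Would the cancelled contact have mattered for rule 5?** Take a patient stopped at the first infusion, and assume that the 30-day visit window (30 to 42 days, Appendix B) is counted from that dose. The first survival contact comes 12 ± 4 weeks later, that is 8 to 16 weeks, or 56 to 112 days.

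- Earliest: 30 + 56 = day 86
- Latest: 42 + 112 = day 154

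SAE reporting ends 30 days after last treatment (Section 9.2.1). Day 86 to 154 is therefore after routine SAE capture and before day 190. A death learned of at that contact would turn a PFS censoring at first dose into an event. If the bullet is followed, that contact does not take place.

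**4. What is not affected?** A patient who reacts to the first Debio 1562 infusion before receiving rituximab is outside the efficacy evaluable population with or without the bullet, because SAP 7.3 requires a dose of both drugs. No effect on ORR is claimed.

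**The case against.** The best defense is that the bullet is loose wording in a table of suggestions. Section 5.10, whose heading speaks of removing patients from the study, opens with treatment discontinuation and continued follow-up, so a site looking up the phrase may land on the right rule. Table 4 is offered as guidance, whereas the follow-up sections are directive, and a careful site would prefer the directive text. The only explicit bar on further data collection in Section 5.10.2 applies to a patient who also withdraws consent for disclosure of future information.

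The effect is also narrow. PFS and OS are secondary endpoints, no comparison between cohorts is planned, and SAP 10.2.1 confines hypothesis testing to the primary efficacy endpoint. Section 4.1.2 allows replacement of patients stopped for hypersensitivity on Day 1 of Cycle 1. Enrollment was complete by this version (Section 1.9), so only patients still on treatment could be affected by a change.

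Most of this limits the size, and it stands on that footing. It does not reconcile the texts. The loose reading makes the last bullet a repeat of the treatment-stop bullet in the same row, and the body of Section 5.10 contrasts removal with continued follow-up. No text ranks the table below the other sections. Investigator decision and the catch-all reason in 5.10.2 give a site a way to record the removal. Replacing a patient does not restore the follow-up of the one who was replaced.

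**Conclusion.** The concern holds. The Grade 4 row of Table 4 contradicts Sections 5.7.5, 5.9.2.1, 5.10.1 and 9.1 and the appendix schedules. That part rests on the wording alone.

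The loss of data is conditional on a site following the bullet rather than the directive sections. Its size cannot be given, because the documents state no Grade 4 infusion-reaction rate. Few patients are likely to be affected: Section 5.7.5 describes Debio 1562 reactions as mild to moderate (severe ones are reported with rituximab), premedication is required, patients unable to tolerate antibody after a prior severe reaction are excluded, and enrollment had closed. On 14 April 2020 three patients were on QW treatment; the number on Q3W treatment is not given. This is a minor correction, worth making because it protects late safety and survival data in the patients with the worst reactions.

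**What to change.** In the Grade 4 row of Table 4, replace the last bullet with: *Continue AE, PK/ADA (if applicable), response and survival follow-up per Sections 5.7.5, 5.10.1 and 9.1 unless the patient withdraws consent.* Leave the treatment-stop bullet unchanged.

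The cost is one bullet. No visit, sample or scan is added, because the replacement only points to follow-up that the protocol already requires.
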